2. OBJECTIVES AND HYPOTHESES

2.1 Primary Objective(s) & Hypothesis(es)

Primary Objectives:

The primary goal of this study is to compare the efficiency of the PLCO_{M2012} >1.58% (6 year risk) risk score and the NELSON inclusion criteria in identifying patients with lung cancer in the age group 55-79 years. To that end, the PLCO_{M2012} model and the NELSON inclusion criteria will be compared

(i) primarily regarding the positive predictive value of lung cancers detected using the two inclusion methods.

2.2 Secondary Objective(s) & Hypothesis(es)

Key-Secondary Objectives:

The PLCO_{M2012} model and the NELSON inclusion method will be compared

(ii) secondarily to the primary objective regarding the following hierarchically ordered key-secondary endpoints:

1. Proportion of individuals selected for screening
2. Proportion of lung cancers detected
3. Sensitivity and specificity of the scores in cancer detection

Secondary Objectives:

The main secondary objectives of this trial is to document that:

1. Reporting of the coronary artery calcium score from low dose computed tomography (LDCT) data will lead to an increase in the rate of preventive cardiovascular treatments and reduced cardiovascular mortality.

Additional objectives are to show that:

1. Effective smoking cessation counselling is implemented as part of the screening program (urine cotinine check in quitters).
2. CT derived information on tobacco related lung destruction, such as emphysema, may influence the smoking cessation rate.
3. Structured reporting of clinically relevant non-cardiac incidental findings, e.g., emphysema or lung fibrosis, will lead to early detection and improved management of diseases.
4. Adding the PanCan algorithm/AI to the LungRads1.1 algorithm for nodule management increases the efficiency.
5. Assessment of various blood-based or exhalation-based biomarkers may provide additional translational information in positive LDCT cases with subsequent biopsy, which may have an impact on the effectiveness of the LDCT test.
6. Cost effectiveness analysis on recruiting strategies, risk models used, effectiveness on smoking cessation and cardiovascular mortality is implemented.

3. METHODOLOGY

3.1 Study Design – General Aspects

The HANSE study is a prospective, randomized comparator controlled population-based screening study.

3.1.1 Data Source(s)

- Low-dose CT: Presence and grade of lung nodules according to LungRADS 1.1 criteria; Coronary calcium scores (Agatston score); Percent lung emphysema (Coreline Software), clinically relevant incidental findings.
- Patient questionnaire.
- Results of blood sample and exhalation sample analysis in LDCT positive patients.
- Lung function test (bodyplethysmography and diffusing capacity of the lungs for carbon monoxide)
- BMI, blood pressure
- Urine cotinine test
- healthcare costs for the HANSE study
- All data will be collected in the HANSE electronic case report form (eCRF)

3.2 Study Population

Male and female subjects age 55-79 years AND history of smoking. Population will be identified via local general population-based registries (“Einwohnermeldeämter”) and informed about the screening study by mail. The registries are general population based local registries (“Einwohnermeldeamt”), where all inhabitants in a region are registered by law. We requested Name, birthdate and address from the 3 participating cities (Hannover, Lübeck and Hamburg) in the age group 55-79. Additional recruitment efforts via local physicians (GPs, specialists) and campaigns targeting the general public.

Mailed information package will contain a response element (paper) with questions concerning their smoking habits and history and link to study website. Interested individuals might either reply using the response element or input their data on the study website. Self-reported health data will be used to pre-qualify subjects based on PLCO / NELSON criteria.

Subjects with preliminary PLCO risk-score $\geq 1.58\%$ (6 years) or NELSON inclusion criteria will be invited to one of the study centers (high-risk group). On site, all subjects will undergo validation of their risk scores, additional examination of their medical condition, medical history and current medication by qualified personnel. Data will be stored in specially designed database (Clinical Research Organisation – CRO).

Subjects, who did not meet the NELSON or PLCO criteria, will be asked to volunteer by contributing long-term outcome data, from regional and national cancer registries informing of the development of lung cancer or death from lung cancer (low-risk group).

Subjects included will be randomized prior to the initial LDCT scan. Randomization will not affect the procedure of the lung cancer screening protocol but only determine the participants

of the coronary calcium score and emphysema score reporting vs. non-reporting group. Randomization ratio of 1:1 and a 2-factorial design (1/4 calc score only; 1/4 emphysema score only, 1/4 both; 1/4 none) will provide equally sized groups of patients in the reporting and non-reporting group.

Randomization will be upheld for the one year CT screening round. Coronary calcium and emphysema scores of the subjects in the non-reporting group will remain confidential during the entire study duration (10 years).

3.3 Inclusion Criteria

1. Male and female subjects aged 55-79 years
2. Current or former smokers
3. Subjects with calculated risk score PLCO₂₀₁₂ $\geq 1.58\%$ (6 yrs.) or NELSON inclusion criteria (current or former smokers [those who had quit ≤ 10 years ago] who had smoked > 15 cigarettes a day for > 25 years or > 10 cigarettes a day for > 30 years).
4. Able and willing to give written informed consent

Volunteers fulfilling all inclusion criteria are undergoing two low dose CT screening rounds (**high-risk group**).

In addition, non-qualifying subjects fulfilling inclusion criteria 1 (age), 2 (smoking history) and 4 (consent), but do not meet the inclusion criterion 3 (risk too low) will be asked to volunteer by contributing long-term outcome data informing of the development of lung cancer or death from lung cancer (n=7100 randomly selected, **low-risk group**). These subjects will be contacted via mail after a minimum of 5 year follow up to inquire if they developed lung cancer in the time between their recruitment and present. Non-responders will be followed by local registries and by phone. New lung cancer cases will be verified using official hospital or cancer registry documents. The 5 year follow up period was chosen to account for the lead-time bias between tumor and symptoms occurrence and cancer diagnosis in the low-risk group.

3.4 Exclusion Criteria

1. Comorbidity, which would unequivocally contraindicate either screening or treatment if lung cancer were detected.
2. History of chest CT within the past year preceding the invitation.
3. Inability to undergo non-contrast CT (e.g. ≥ 200 kg body weight, inability to lie flat).
4. Pregnancy
5. Risk of non-compliance with study procedures.
 - Unable to give written consent

- Patient's inability to fill in the questionnaire self-dependent
- Limited knowledge of the German language
- Inability to travel, residents of care facilities, etc.

4. VARIABLES AND EPIDEMIOLOGICAL MEASUREMENTS

4.1 Exposures

4.1.1 Definition of Primary Exposure

Recruited volunteers in the high-risk group undergo 2 low-dose CT screening rounds (baseline and 1 year follow up).

4.1.2 Definition of Comparison Exposure

The low-risk group will not receive low-dose CT screening. They will be contacted after 5 years to inquire if they developed lung cancer in the time between their recruitment and present. Non-responders will be followed by local registries and by phone.

4.2 Outcomes

Primary endpoints:

1. Proportion of lung cancers detected with different risk models

To address the suitability of different inclusion methods for identifying the high-risk population for screening, the PLCO_M2012 model and the NELSON inclusion criteria will be compared primarily for the positive predictive value of lung cancers detected within the study population after 2 screening rounds.

Key-Secondary endpoints:

Additionally, the PLCO_M2012 model and the NELSON inclusion criteria will be compared in a hierarchical order regarding the key secondary endpoints:

1. Proportion of individuals selected for screening within the high-risk study population
2. Proportion of lung cancers detected with different inclusion methods (NELSON vs. PLCO) within the overall study population after 5 years
3. Proportion of lung cancers detected within the high-risk population
4. Sensitivity within the overall population after 5 years.

5. Specificity within the overall population after 5 years.

Secondary endpoints:

6. **Rate of initiation of cardiovascular treatments** (in particular lipid-lowering) in the calcium score reporting group vs. the non-reporting group after year 1 of study.
7. **Efficiency of nodule management algorithms:** Based on the two alternative management algorithms (LungRads1.1 alone or LungRads1.1 + PanCan/AI) participants are sorted into three management groups: (a) next surveillance scan, (b) early recall scan, or (c) diagnostic evaluation recommended. For one algorithm to be more efficient, the following criteria must both be fulfilled
 - i. The number of participants without cancer sorted in the category (a) is higher AND
 - ii. The number of participants with lung cancer sorted into category (b) or (c) is higher.
8. **Success of screening program.** Based on all individuals enrolled. Definition of success is calculated using:
 - a. Response rate (1. Respondents to questionnaire / invitation: those who send their smoking history & other relevant data; 2. among the above respondents, those who are eligible by one of the two criteria, or both; 3. those who are eligible, and actually take part in the screening), number of drop-outs, effectiveness of patient recruitment via mailings vs. GPs referrals (individual response rates)
 - b. Reliability of PLCO risk scoring (self-reported vs. on site assessment)
 - c. Percentage of subjects receiving an adequate low-dose CT scan and report according to DRG guidelines (number of diagnostic CTs/number of all CTs)
 - d. Percentage of subjects receiving adequate follow-up procedures
9. **Quality of screening program.**
 - a. CT reading performance (2nd reader vs. CAD vs. AI, positive predictive value)
 - b. Quality of lung nodule management
 - c. Frequency of detection and management of incidental findings from low dose chest CT (emphysema, coronary heart disease, etc.)
 - d. LDCT dose management

10. Smoking cessation

- a. Success of smoking cessation counseling based on number of participants quitting with or without revealing additional health risks (emphysema score, coronary calcium score or both).

11. Blood-based and exhalation-based biomarkers

- a. Evaluation of various blood-based or exhalation-based biomarkers in positive LDCT cases with subsequent biopsy on the positive predictive value of the LDCT test:

Liquid Biopsy:

- Epigenetic Signature Profile from cell free DNA (currently 835 loci), a more specific description is possible after patent approval.

Exhaled Breath Condensates:

- RNA Analysis of the genes TUBA1A and HPRT, followed by analysis for GATA6 Em, GATA6 Ad, NKX2-1 Em, NKX2-Ad.

12. Cost-effectiveness analysis

- a. Cost-effectiveness modeling to investigate the impact of different components of LDCT lung cancer screening on the long-term all-cause mortality and cost-effectiveness: Key components include risk score-based selection criteria, nodule management protocols, threshold values of imaging biomarkers for cardio-vascular diseases and COPD, and inclusion of smoking cessation programs (CHERH).
- b. Comparison of patient recruitment strategies: Cost-effectiveness of register-based mailing campaign vs. GP referrals in terms of recruitment of qualified screening subjects (CHERH).

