BACKGROUND /RATIONALE:	
Germany has a long history of offering screening programs for cancers, such as breast, colorectal, and, more recently, cervical and skin cancer. Screening for lung cancer, however, which causes more deaths than any other cancer in men and is the second leading cancer death in women (not far behind breast cancer), has not been implemented to date.
 
Only very recently, IQWiG in a preliminary assessment of low-dose CT screening, concluded that the benefits from screening outweigh potential risks. However, an implementation of a national lung cancer screening program, which would be covered by the general health insurance, will likely not be implemented before 2022. Nonetheless, the IQWiG report also comments on important criteria for implementing lung cancer screening in Germany using low-dose CT:
 
1. It would be necessary to determine criteria that define a high-risk population. Various risk forecasting models are currently being propagated to enable a more precise selection of high-risk individuals. Their reliability and repeatability needs to be checked.2. Integration of access to a smoking cessation program.3. Quality assurance measures must be taken into account, including standardized protocols for the evaluation of the CT images and the subsequent follow-up checks as well as the invasive diagnostic tissue sampling procedures. 
The HANSE study is primarily intended as a pilot to provide evidence that a holistic and effective lung cancer screening program can be implemented in Germany and that such a screening program can be integrated in the current infrastructure of certified lung cancer centers.

OBJECTIVE(S)	
Primary Objectives: The primary goal of this study is to compare the efficiency of the PLCO_{M2012} >1.58% (6 year risk) risk score and the NELSON inclusion criteria in identifying patients with lung cancer in the age group 55-79 years. To that end, the PLCO_{M2012} model and the NELSON inclusion criteria will be compared (i) primarily regarding the positive predictive value of the two inclusion methods for lung cancers detected after 2 screening rounds in the study population and
 
Secondary Objectives: (ii) secondarily regarding the following hierarchically ordered key-secondary endpoints: 1. Proportion of individuals selected for screening

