--	--

	
points in the cardiovascular treatment rate. Acknowledging that only 44% of all patients are assumed to show CAC on low dose CT, the expected difference between the reporting and non-reporting group is $(73\%-68\%) * 44\% = 2.2\%$. Equivalently, the assumed rate ratio between the reporting and non-reporting group is $(73\% * 44\%) / (68\% * 44\%) = 1.07$. With 2500 patients randomized to each arm and using a Chi-Square Test with a two-sided type-I-error rate of 5% for testing the null-hypothesis of no difference between the groups, the statistical power is 97%.
 
(iii) To evaluate the power of potential longitudinal follow-up studies based on this screening trial, the power for the 10 year mortality endpoint has been calculated based on the results of the NELSON study using a Chi-Square Test with a two-sided type-I-error rate of 5% for testing the null-hypothesis of no difference in 10-year mortality rates between the reporting and non-reporting groups. In line with the results of the NELSON study, we assume a 10 year cardiovascular mortality rate in the non-reporting group of 2.7%. Assuming a rate ratio of 0.6 between the reporting and non-reporting group (or equivalently, a 10-year mortality rate of 1.6%), the difference between the reporting and non-reporting group can be shown with a power of 75%.
 
In order to include 5000 volunteers in the high-risk group in the HANSE study 5500 need to be recruited to account for drop outs (10%).
 
Conclusion: With an overall sample size of 5,000 subjects (and 2500 volunteers randomized to the reporting and non-reporting group) the study is well-powered to investigate the primary hypothesis, evaluate potential cardiovascular benefit and provide the basis to investigate mortality in a follow-up study.

SAMPLE SIZE	
To be assessed for eligibility: n = 350 000 To be allocated to trial: n = 5500 + all recruited volunteers with low risk scores/low NELSON criteria (low risk group) To be analysed: n = 5000 + 7100 low risk group

TRIAL DURATION	
First patient in to last patient out (months): 30 Duration of the entire trial (months): 36 (longitudinal extension up to 10 years) Recruitment period (months): 12

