For testing the null-hypothesis of no difference between the risk scores regarding the proportion of individuals selected for screening, McNemar's Test will be used.

Description of the primary analysis and population:

The primary analysis will be conducted of all volunteers within the overall study population after 2 LDCT screening rounds.

5.1.2 Secondary Objective(s): Calculation of Epidemiological Measure(s) of Interest (e.g. hazard ratios, incidence rates, test/retest reliability)

1. Rate/rate ratio of initiation of cardiovascular treatments (in particular lipid-lowering) in the calcium score reporting group vs. the non-reporting group after year 1 of study:

2. Efficiency of nodule management algorithms:

Based on the two alternative management algorithms (LungRads1.1 alone or LungRads1.1 + PanCan) patients are sorted into three management groups: (a) next surveillance scan, (b) early recall scan, or (c) diagnostic evaluation recommended. For one algorithm to be more efficient, the following criteria must both be fulfilled

- i. The number of patients without cancer sorted in the category (a) is higher AND
- ii. The number of patients with lung cancer sorted into category (b) or (c) is higher.

3. Success of screening program. Based on all individuals enrolled. Definition of success is calculated using:

a. Response rate (number of responses/overall number contacted), number of drop-outs, effectiveness of patient recruitment via mailings vs. GPs referrals (individual response rates)

b. Percentage of subjects meeting all inclusion/exclusion criteria

c. Repeatability of the PLCO score

d. Percentage of subjects receiving an adequate low-dose CT scan according to DRG guidelines (number of diagnostic CTs/number of all CTs)

4. Quality of screening program.

a. CT reading performance (2nd reader vs. CAD vs. AI)

b. Frequency of detection and management of incidental findings from low dose chest CT (emphysema, coronary heart disease, etc.)

c. Subsequent identification of biomarkers with predictive value / correlation with positive LDCT findings / cancer risk

5. Smoking cessation

a. Success of smoking cessation counseling based on number of participants quitting with or without revealing additional health risks (emphysema score, coronary calcium score or both).

6. Blood-based and exhalation- based biomarkers

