5.2 Bias

5.2.1 Methods to Minimize Bias

Randomization: Subjects included in the screening study will be randomized prior to receiving the initial LDCT scan. Randomization will not affect the procedure and the schedule of the cancer screening process but only determine the allocation of the participants of the coronary calcium score and emphysema score to the reporting and the non-reporting group. Randomization ratio of 1:1 and a 2-factorial design ($\frac{1}{4}$ calcium score only; $\frac{1}{4}$ emphysema score only, $\frac{1}{4}$ both; $\frac{1}{4}$ none) will provide equally sized groups of patients in both groups including age and sex stratification.

Sampling bias: To minimize sampling bias we randomly select volunteers in the age group 55-79 from the local general population registry database (“Einwohnermeldeämter”) to be contacted via mail at each study center. Additional recruitment efforts via GP or public media may introduce a sampling bias; however, this recruitment strategy reflects the real world setting of a future German national lung cancer-screening program. Additionally, we will track and analyze the recruitment pathways in the HANSE study.

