5.2.2 Adjustment for Multiple Comparisons

The primary and key-secondary endpoints will be tested in a hierarchical order, thereby controlling the overall type-I error rate at 5%. Therefore, no correction of p-values for multiple testing needs to be performed. All secondary parameters will be considered explorative.

Strengths and Limitations

Strengths

Importantly, the results and the innovative workflow infrastructure of this study should pave the way for an effective comprehensive screening program in Germany. Especially, novel results about the definition of the high-risk population, the inclusion of cardiovascular and lung comorbidity, smoking cessation and cost-effectiveness will guide the future German lung cancer screening program.

Limitations:

This study is designed as a reference case for a nationwide lung cancer screening program, which both suffer from limitations. The voluntary participation may introduce a certain bias and may not reveal all high-risk cases. In addition, clinically not apparent lung cancer cases in the low-risk population will be missed, since this group will not receive a LDCT. However, we follow-up smokers, who did not meet the risk score inclusion criteria and were willing to participate in the study, after 5 years to calculate the proportion of clinically detected lung

cancers, which were missed due to non-inclusion in the high risk group. This will generate important data for the ethical and economical discussion of risk-based inclusion for lung cancer screening.

The assessment of coronary calcium scores is usually performed on normal dose ECG-gated CT. However, recently it has been shown that coronary artery calcium scoring is feasible on non-ECG-gated LDCT. Furthermore, the used Coreline software has an innovative and fully automated algorithm especially developed for non-ECG gated Coronary calcium score on LDCT.

Due to the 36 month time horizon of the study, the endpoint ‘initiation of cv treatment’ was selected, rather than a clinically more meaningful endpoint, such as 10 year cardiovascular mortality, for example. However, the investigators will seek additional funding to continue the coronary calcium part of the study in order to evaluate cardiovascular and all-cause mortality at year 10 follow-up.

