5.3 Sample Size and Power Calculations

To be assessed for eligibility: n = 350 000

To be allocated to trial: n = 5500 + all recruited volunteers with low risk scores/low NELSON criteria (low risk group)

To be analysed: n = 5000 + 7100 low risk group

(i) Power calculation for the primary endpoint

Sample size calculation is based on data from the German Health Update study (GEDA; “Gesundheit in Deutschland aktuell”) - a health monitoring program consisting of cross-sectional surveys conducted by the Robert Koch Institute to provide data on health and disease, health determinants and health behaviors from nationally representative samples of adults in Germany (20). Between 2008 and 2013, three GEDA studies were carried out, in 2008–2009, 2009–2010 and 2012–2013, involving a total of 62,606 computer assisted telephone interviews (23, 24). Based on this dataset the PLCO risk score was adjusted to a level (5-year risk of 1.314%, or 6-year risk of 1.58% [rounded]) were the NELSON inclusion criteria and the PCLO risk score are equally weighted in the German population aged 55–79 to include the same amount of volunteers in each group (table 3)

Table 3:

Risk threshold of 0.01314 (5y risk, weighted, scaled to 5000 participants) - Eversmokers aged 55-79				
Nelson				
	0		1	
PLCO	0 7095.8 (21.8)	1070.25 (9.8)		
	1 1072.73 (27.0)	2857.04 (112.2)		

Number of ever smokers (predicted cancers) GEDA dataset (23, 24).

Between parentheses are the 5-year case numbers predicted by the PLCO model.

In a study by Hüsing & Kaaks (24) this model was found to accurately predict absolute lung cancer incidence compared to incidence actually observed (cancer registry data).

However, for power calculations one cannot directly assume that predicted 5-year incidence corresponds to the number of LC cases that will be detected by two CT screenings over a 1-year interval.

To estimate the number of expected CT-detected cases (two screens, 1-year interval) we extrapolated from observations in the LUSI trial. LUSI included participants 50-69 years of age who met the smoking criteria of NELSON. In a total of 2029 participants in the screening arm, 34 LC cases were detected in the first two screening rounds (22 at prevalence screen, and 12 at the first incidence screen).

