6.1.2 Procedures

Figure 2: Procedure workflow of the Hanse Study

1. Recruitment

- Population will be contacted by mail (address data of individuals in the age group obtained from local population registries) with an **individually tailored invitation letter** and response element (paper and website) to assess their overall qualification and willingness to participate. Additional recruitment efforts via local physicians (**GPs**), and via **public media** using the study website.

Age	
Gender	
Race/ethnicity	
Education	
Height	
Weight	
Chronic obstructive pulmonary disease (yes vs. no)	
Prior diagnosis of pneumonia (yes vs. no)	
Prior diagnosis of emphysema (yes vs. no)	
Prior diagnosis of bronchitis (yes vs. no)	
Prior diagnosis of tuberculosis (yes vs. no)	
Personal history of cancer (yes vs. no)	
Family history of lung cancer (yes vs. no)	
Early onset vs. late onset	
Smoking status (former=0, current=1)	
Former smoker (yes vs. no)	
Current smoker (yes vs. no)	
Smoking intensity (average cigarettes/day)	
Smoking duration (years)	
Smoking quit-time	
Chest CT within past year (yes vs. no)	
Pregnancy yes/no	
Any comorbidities (free text)	
Ability to travel to the screening center	

Table 5: Variables for risk scoring, applicable for PLCO model

- Initial eligibility assessment based on self-reported data (age, smoking history and parameters required for the NELSON inclusion criteria and PLCO scores, table 5) in return letter, based on individuals' input in study website, or according to GP assessment. Data of eligible subjects will be stored in CRO database. Eligible subjects (based on initial assessment of risk) will receive an invitation for participation in the screening program with additional background information.
- On site validation of variables required for risk scoring models and accompanying assessment of medical condition, medical history, current medication by qualified medical staff.
- Data will be stored in database (CRO) and PLCO_{M2012} risk score and NELSON inclusion criteria will be determined. Individuals with PLCO_{M2012} risk score $\geq 1.58\%$ (6 yrs.) or NELSON inclusion criteria will be included in the study.

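### The first key-secondary test asks whether the two rules select different numbers of people, although the PLCO threshold was set to make those numbers equal; this can block every 5-year confirmatory comparison

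*Protocol*

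**What the plan says.** The Protocol fixes the testing order itself. The synopsis objectives refer to "hierarchically ordered key-secondary endpoints: 1. Proportion of individuals selected for screening". The synopsis outcomes, section 2.2 and section 4.2 also list this endpoint first, in 4.2 as "Proportion of individuals selected for screening within the high-risk study population". The proportion of lung cancers detected in the overall population at 5 years comes next.

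Section 5.2.2 states: "The primary and key-secondary endpoints will be tested in a hierarchical order, thereby controlling the overall type-I error rate at 5" per cent. It concludes that no p-value correction is needed. No text lets the sequence continue after a non-significant step.

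Section 5.1.1 defines the two proportions selected as (A+B)/(A+B+C) for PLCO and (A+C)/(A+B+C) for NELSON. It assigns McNemar's test to the null hypothesis of "no difference between the risk scores regarding the proportion of individuals selected for screening".

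Section 5.3 (i) says the PLCO threshold was adjusted on GEDA data "to include the same amount of volunteers in each group". Table 3 gives 1072.73 people positive by PLCO only and 1070.25 by NELSON only. Section 5.3 gives no effect size or power for this endpoint.

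The statistical text carries the order less clearly than the lists do. Both the synopsis and section 5.1.1 introduce cancers detected directly after PPV as the secondary analysis, then defer to the hierarchy set out earlier. The synopsis outcomes also reverse sensitivity and specificity relative to section 4.2, which is an editorial matter.

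**The concern.** In a fixed sequence at full alpha, a non-significant step ends confirmatory testing. Here the first step after the primary has a null hypothesis that the design deliberately makes nearly true: the threshold was chosen so that B is about C, and the test then has to show that B differs from C before anything later can be claimed. The intended calibration result therefore counts as failure.

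If the gate does open, that reflects the mix of people who volunteered. Section 5.2.1 itself warns: "Additional recruitment efforts via GP or public media may introduce a sampling bias". Neither a closed nor an open gate says which rule finds more cancers. At stake is the confirmatory status of the 5-year comparisons, for which about 7100 low-risk volunteers are to be followed.

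**Working it through.** **Inputs (Protocol section 5.3 and Table 3).** High-risk N = 5000. Multinomial weights are 2857 (both rules, A), 1070 (NELSON only, C) and 1072 (PLCO only, B), rescaled because they sum to 4999. Cancer probabilities are (144/149)(112/2857) = 0.0379 for both, (144/149)(10/1070) = 0.0090 for NELSON only and (144/149)(27/1072) = 0.0243 for PLCO only. Tests are two-sided at 5%.

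**Primary test.** The weighted generalized score statistic is T = (PPV1 − PPV2)² / {[p(1−p) − 2Cp](1/n1 + 1/n2)}, with n1 = A+B, n2 = A+C, pooled p = (2a+b+c)/(n1+n2) and Cp = [a(1−p)² + (A−a)p²]/(n1+n2), referred to chi-square with 1 df.

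**Reproducing the Protocol's figures.** The expected number of CT-detected cases is 34 × 5000/2029 × 1.72 = 144.1 (stated 144). The PPV ratio is 1.140 (stated 14% higher). Simulated primary power over 400,000 runs is 79.9% (stated 80.3%).

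**What the gate tests.** The two proportions share a denominator, so their difference is (B−C)/(A+B+C) and the null is B = C. At the planned counts:

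- difference = 2.48/5000 = 0.05 percentage points;
- standard error = √(1072.73+1070.25)/5000 = 46.29/5000 = 0.93 points;
- 95% CI −1.8 to +1.9 points;
- McNemar noncentrality = 2.48/46.29 = 0.05, so the rejection probability is 5.0%, essentially alpha.

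Significance needs |B−C| of about 1.96 × 46.29 = 90.7, i.e. a 52.1:47.9 split of the discordant participants.

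**Joint probability when volunteers match GEDA.** Primary 79.86%; gate 5.04% (PLCO larger 2.79%, NELSON larger 2.25%); both 3.94%. The gate's own loss is 79.86 − 3.94 = 75.92 points. The other 20 points are lost at the primary. With exact or continuity-corrected McNemar the joint figure is 3.7%.

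**When the recruited mix departs from GEDA.** The PLCO-only share of the 2142 discordant participants is varied as an assumption, with cancer rates per cell held at their section 5.3 values:

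| PLCO-only share | Gate opens | Primary significant | Both | Lost to gate (points) |
|---|---|---|---|---|
| 45% | 99.7% | 92.8% | 92.5% | 0.3 |
| 46% | 96.0% | 91.1% | 87.6% | 3.5 |
| 47% | 79.4% | 88.9% | 71.4% | 17.5 |
| 48% | 45.8% | 86.4% | 40.8% | 45.7 |
| 49% | 15.3% | 83.4% | 13.5% | 69.9 |
| GEDA (about 50%) | 5.0% | 79.9% | 3.9% | 75.9 |
| 51% | 15.2% | 76.4% | 10.6% | 65.8 |
| 52% | 45.8% | 72.2% | 31.2% | 41.0 |
| 53% | 79.5% | 67.6% | 52.3% | 15.3 |
| 54% | 95.9% | 63.0% | 60.0% | 3.0 |
| 55% | 99.6% | 58.0% | 57.7% | 0.3 |

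A 54:46 split is a difference of 0.08 × 2142 = 171 people of 5000.

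**What is blocked.** On Table 3, cancers detected overall are (112.2+27.0)/170.8 = 81.5% for PLCO and (112.2+9.8)/170.8 = 71.4% for NELSON. Within the high-risk group they are 139.2/149.0 = 93.4% and 122.0/149.0 = 81.9%. Both comparisons rest on the same discordant cancers, 27.0 and 9.8, so they give the same McNemar statistic. Its power is about 83% asymptotically and 78% exactly. This is illustrative only, because Table 3 holds model predictions without screening.

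Specificity compares non-cancer discordants of 1072.73 − 27.0 = 1045.7 and 1070.25 − 9.8 = 1060.5, which gives power of about 6%.

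**The case against.** The best defence has four parts.

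- **The 4% is the worst point.** It requires volunteers to match GEDA almost exactly. GEDA is 2008 to 2013 survey data, the threshold was moved from 5 to 6 years by assumed linearity (1.314 × 6/5 = 1.577, rounded to 1.58), and GP and media recruitment can shift B against C. This stands as a limit on the size, and the table shows how quickly the cost falls. It does not rescue the gate: opening because recruitment drifted is not a sensible condition for testing cancer detection.
- **The primary nearly answers the same question.** When B is close to C, the PPV denominators nearly match. In simulation at the GEDA mix, McNemar on b versus c was also significant in 97% of runs where the primary succeeded and the gate stayed closed. That limits the practical loss, but it concerns cancers found in two rounds. It gives no confirmatory status to the 5-year comparison, which adds later cancers and was not modelled.
- **A fixed sequence is valid at any power.** True. Type-I error is controlled, the Protocol claims no power for any key secondary, and every estimate can still be reported. The fault is in the ordering.
- **The endpoint is available early.** The synopsis gives "Duration of the entire trial (months): 36 (longitudinal extension up to 10 years". If cancers detected in the high-risk group is read as a 5-year endpoint, as the synopsis has it, proportion selected is the only key secondary available in that time; section 4.2 sets no time for that item. Early availability justifies early reporting, not a gate.

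**Conclusion.** The concern holds and should be fixed. All the listed hierarchies make the 5-year claims depend first on a test for which the design plans no difference. If volunteers match GEDA, the chance of reaching the next key secondary is 3.9% instead of 79.9%. The cost is 41 to 46 points at a 52:48 split in either direction, 15 to 18 points at 53:47 and about 3 points at 54:46. These figures rest on the section 5.3 model, on cell-specific cancer rates that stay fixed as the mix changes, and on the sequence stopping at the first non-significant result. The primary PPV test is not affected. What is lost is formal status for the comparison of cancers detected, not the ability to estimate it.

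**What to change.** Take proportion selected out of the confirmatory sequence and report it with a 95% confidence interval alongside the primary, as a check on the calibration. One workable order is:

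1. PPV after two screening rounds;
2. proportion of lung cancers detected in the overall population at 5 years;
3. specificity at 5 years.

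Report cancers detected within the high-risk group (read at 5 years) and overall sensitivity without steps of their own: the first uses the same discordant cells as step 2, and section 5.1.1 equates the second with it. Placing proportion selected last would also free step 2. It is the weaker option, because proportion selected would then sit behind a specificity step with about 6% power on Table 3.

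State the same order in the synopsis (objectives, outcomes and statistical analysis) and in sections 2.2, 4.2 and 5.1.1.

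The cost is an amendment to the testing order, with no new data, procedures or participants. The sponsor gives up an early formal claim on proportion selected; if it is placed last, that claim waits until at least year 5. The order must be fixed before B and C are tabulated. Under section 6.1.2 the "risk score and NELSON inclusion criteria will be determined" as people enrol, so the deadline is before anyone looks at those counts, not merely before enrolment ends.
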